13.13 End of Study Definition

The end of the double-blind, placebo-controlled period of the study is defined as the completion of the last follow-up visit of the last enrolled subject who elects not to participate in the OLE period of the study.

For subjects electing to enter the OLE period of the study, the end of the OLE period of the study is defined as the completion of the last follow-up visit for the last subject.

The enrollment of the last subject in the double-blind period of the study is anticipated to occur in the first half of 2023. The last subject's last follow up visit will be approximately 24 weeks after the date of enrollment if OLE is not elected, or up to 38 weeks after the date of enrollment if the OLE is elected.

Please refer to Section [14.12](#) for the study ending prematurely.

14. Adverse Event Reporting and Documentation

14.1 Adverse Events

In accordance with 21 Code of Federal Regulation (CFR) 312.32(b) and International Conference on Harmonization (ICH) Guidance E2A, an AE is any untoward medical occurrence in a clinical investigation of a subject administered a pharmaceutical product and that does not necessarily have a causal relationship with the treatment.

An AE is therefore any unfavorable and unintended sign (including an abnormal laboratory finding), symptom, or disease temporally associated with the administration of an investigational product, whether or not related to that investigational product. An unexpected AE is one of a type not identified in nature, severity, or frequency in the current Investigator's Brochure or of greater severity or frequency than expected based on the information in the Investigator's Brochure.

Examples of an AE include:

- Significant worsening or exacerbation of underlying medical condition.
- Significant abnormal findings from physical exams, vital signs, or laboratory tests.

The following examples are not considered AE:

- Medical or surgical procedure, although the condition leading to the procedure is usually an AE.
- Anticipated day-to-day fluctuations of preexisting medical conditions (including laboratory values) as long as significant worsening from baseline does not occur.
- Signs or symptoms of the disorder being studied unless they become more severe or occur with greater frequency than occurring at baseline.

All AE, whether elicited by questions from study staff, volunteered, or noted on physical examination/laboratory testing, and regardless of causality or severity, will be assessed and recorded in the eCRF beginning after the first administration of study drug in the double-blind period of the study and ending at the time of study completion or ET of the double-blind period or the OLE period, whichever is later.

For subjects participating in the OLE period, AE will be recorded in the CRF of the AK002-018 double-blind treatment period database up until the first administration of lirentelimab in the OLE period and recorded in the CRF of the AK002-018 OLE period database beginning from the time of first administration of lirentelimab ending at the time of study completion or ET of the OLE period.

14.2 Serious Adverse Events

A SAE is defined as an AE that meets that one of the following criteria:

- Death
- A life-threatening AE that places the subject at risk of death at the time of the event. It does not refer to an event that hypothetically might cause death if it were more severe.
- Inpatient hospitalization or prolongation of existing hospitalization.
- A persistent or significant disability/incapacity.
- A congenital anomaly/birth defect occurring in the offspring of a study subject.
- Other important medical events may also be considered a SAE when, based on appropriate medical judgment, they jeopardize the subject or require intervention to prevent any of the outcomes listed above.

Serious adverse events will be assessed and recorded beginning after the first administration of study drug in the double-blind period and ending at the time of study completion or ET of the

double-blind period or the OLE period, whichever is later. If the SAE is related to a screening procedure, it will be captured from the date of the screening procedure.

14.3 Adverse Events of Special Interest

Adverse Events of Special Interest (AESI) for this study include:

- Malignancies confirmed by histopathological report. (Mast cells and eosinophils are part of the normal immune response. By decreasing their function, lirentelimab could theoretically increase the risk of malignancy.)
- Parasitic infections confirmed by positive clinical laboratory test. (Eosinophils are believed to be involved in protecting the body from parasitic infections. Decreasing their function could theoretically increase the risk of parasitic and opportunistic infections.)
- Opportunistic infections (infections known to be more severe or occur more frequently in immunosuppressed populations) as confirmed by positive clinical laboratory test.
- Injection-related reactions and hypersensitivity reactions, including anaphylaxis.

Adverse Events of Special Interest will be assessed beginning after the time of first administration of study drug and ending at the time of study completion or ET of the double-blind period or the OLE period, whichever is later. Any new AESI (or new information related to a previously reported AESI) must be recorded in the AE eCRF and designated as an “AE of special interest.”

14.4 Injection-Related Reactions

All AE considered by the Investigator *to be related* to the biological substance and occurring within 24 hours of the start of the SC injection of study drug should be captured as 1 IRR.

Common symptoms of IRR may include but are not exclusive to:

| | |
|---------------------------------|----------------|
| • Flushing | • Nausea |
| • Chills | • Vomiting |
| • Back or abdominal pain | • Sweating |
| • Chest discomfort or tightness | • Fever |
| • Dizziness | • Urticaria |
| • Shortness of breath | • Pruritus |
| • Headache | • Bronchospasm |

- Hypotension or hypertension

All symptoms experienced by a subject during an IRR will be listed in the eCRF under 1 IRR, unless the Investigator believes a symptom is not part of the IRR, in which case it will be recorded separately. The start time of the IRR will be captured as the start time of the first symptom, and the end time of the IRR will be captured as the end time of the last symptom.

14.5 Injection Site Reactions

All AE considered by the Investigator to be ***related to the SC administration*** of the biological substance ***at the injection site*** and occurring within 24 hours of the start of the injection should be captured as one injection site reaction (ISR).

Common symptoms of ISR include, but are not exclusive to:

- Redness at the injection site
- Itching at the injection site
- Pain at the injection site
- Swelling at the injection site (beyond the bump caused by the volume of drug injected under the skin)
- Bruising at the injection site
- Burning at the injection site

All symptoms experienced by the subject during an ISR will be listed in the eCRF under 1 ISR, unless the Investigator believes a symptom is not part of the ISR, in which case it will be recorded separately. The start time of the ISR will be captured as the start time of the first symptom, and the end time of the ISR will be captured as the end time of the last symptom.

14.6 Anaphylaxis

A suspicion of anaphylaxis will be carefully monitored and treated according to standard of care. Emergency crash cart equipment and medications, including multiple doses of epinephrine, vasopressors, and bronchodilators, will be available at all times during the conduct of the study. To define anaphylactic reactions in a consistent and objective manner, all AE of suspected anaphylaxis will be evaluated using Sampson's Criteria for Anaphylaxis ([Appendix 9](#)). The assessment of an AE will be done pursuant to definitions set forth by ICH Good Clinical Practice (GCP) guidelines and applicable regulatory requirements.

If a subject experiences signs or symptoms of anaphylaxis, they should be treated with standard of care, such as diphenhydramine, acetaminophen, methylprednisolone, epinephrine, and other supportive measures along with cessation of the SC injection. A sample of blood should be obtained for plasma histamine level and tryptase within 1–2 hours of the onset of symptoms. Also, an unscheduled ADA blood sample may be obtained if an immunogenicity-related AE is suspected.

14.7 Evaluating Adverse Events and Serious Adverse Events

14.7.1 Establishing Diagnosis

Whenever possible, diagnoses should be given when signs and symptoms are due to a common etiology (e.g., dysuria, urinary nitrites should be reported as a urinary tract infection). If the diagnosis is not known, individual signs and symptoms should be assessed and recorded in the AE eCRF as separate AE. The Investigator (or qualified Subinvestigator) must assign the following AE attributes listed below (Table 3, Table 4, and Table 5) and is responsible for ensuring this information is recorded in the source documentation.

14.7.2 Assessment of Intensity

Investigators will use their clinical judgment as well as the guidelines laid out in the NCI CTCAE (version 5.0 or most current version) tables (Table 3 and [Appendix 8](#)) to assess the intensity of each AE and SAE.

Table 3 Adverse Event Severity per CTCAE

| Grade | CTCAE Description* |
|-------|--|
| 1 | Mild; asymptomatic or mild symptoms; clinical or diagnostic observations only; intervention not indicated. |
| 2 | Moderate; minimal, local, or noninvasive intervention indicated; limiting age appropriate instrumental activities of daily living (ADL). |
| 3 | Severe or medically significant but not immediately life-threatening, hospitalization or prolongation of hospitalization indicated; disabling; limiting self-care ADL. |
| 4 | Life-threatening consequences, urgent intervention indicated. |
| 5 | Death related to AE. |

* CTCAE v. 5.0: Grade refers to the severity of the AE. The CTCAE displays Grades 1–5 with unique clinical descriptions of severity for each AE based on this general guideline.

The term “severe” is a measure of intensity, and a severe AE is not necessarily a SAE. When the intensity of an AE changes within the same day, the maximum severity for the event should be

entered into the AE eCRF. If the intensity changes over a number of days, these changes should be recorded separately (i.e., as having distinct onset dates).

14.7.3 Assessment of Causality to Study Drug

The Investigator should use their clinical judgment as well as the guidelines in Table 4 to assess the relationship between study drug and AE.

Table 4 Adverse Event Relationship to Study Drug

| Relationship to Study Drug | Comment |
|----------------------------|--|
| Related | There is clear evidence that the event is related to the use of study drug (e.g., confirmation by positive re-challenge test, if possible). Another etiology is considerably less likely. |
| Possible | The event cannot be explained by the subject's medical condition, concomitant therapy, or other causes, and there is a plausible temporal relationship between the event and study drug administration. |
| Unlikely/Remote | An event for which an alternative explanation is more likely (e.g., concomitant medications or ongoing medical conditions) or the temporal relationship to study drug administration and/or exposure suggests that a causal relationship is unlikely. (For reporting purposes, Unlikely/Remote will be grouped together with Not Related.) |
| Not Related | The event can be readily explained by the subject's underlying medical condition, concomitant therapy, or other causes, and therefore, the Investigator believes no relationship exists between the event and study drug. |

14.7.4 Assessment of Causality to Study Procedure

The Investigator should use their clinical judgment as well as the guidelines in [Table 5](#) to assess the relationship between study procedure and AE. Assessment of causality to study procedure should include causality to such items as blood draw (as appropriate), or other.

Table 5 Adverse Event Relationship to Study Procedure

| Relationship to Study Procedure | Comment |
|---------------------------------|---|
| Related | There is clear evidence that the event is related to a study procedure. |
| Possible | The event cannot be explained by the subject's medical condition, concomitant therapy, or other causes, and there is a plausible temporal relationship between the event and a study procedure. |
| Unlikely/Remote | An event for which an alternative explanation is more likely (e.g., concomitant medications or ongoing medical conditions) or the temporal relationship to any study procedure suggests that a causal relationship is unlikely (For reporting purposes, Unlikely/Remote will be grouped together with Not Related). |
| Not Related | The event can be readily explained by the subject's underlying medical condition, concomitant therapy, or other causes, and therefore, the Investigator believes no relationship exists between the event and a study procedure. |

14.7.5 Action Taken

Action taken with respect to study drug will be categorized as none, study drug permanently discontinued, study drug temporarily withdrawn, or other (specify).

Action taken with respect to study participation will be categorized as none, withdrawal from study participation, or other (specify).

Action taken with respect to treatment of an AE will be categorized as none, concomitant medication, concomitant procedure, or other (specify).

14.7.6 Assessment of Outcome

Event outcome at resolution or time of last follow-up will be recorded as: recovered, recovering, not recovered, recovered with sequelae, fatal, or unknown.

14.8 Adverse Event Reporting Procedures

14.8.1 All Adverse Events

Any clinically significant AE that is ongoing at the time of study completion or ET will be followed by the Investigator until event resolution, the AE is otherwise explained, not considered clinically significant by the Investigator, or the subject is lost to follow-up.

All AE identified, whether serious or non-serious, will be recorded in the AE eCRF beginning from the first administration of study drug in the double-blind period of the study and ending at

the time of study completion or ET of the double-blind period or the OLE period, whichever is later. Serious adverse events considered related to screening procedures will be recorded in the AE eCRF starting on the date of informed consent. Whenever appropriate, the CTCAE (version 5.0 or most current version) should be utilized for naming common AE ([Appendix 8](#)).

14.8.2 Serious Adverse Event Reporting

In the event of any SAE reported or observed during the study, whether or not attributable to the study drug, site personnel must report it immediately (**within 24 hours of becoming aware of the SAE**) by fax or email to the Sponsor, Allakos Inc.

The SAE report forms will be provided to the investigational site to assist in collecting, organizing, and reporting SAE, and forms must be completed with as much information as is available and should be submitted to the Sponsor within 24 hours of becoming aware of the SAE. Serious adverse events must also be recorded on the AE eCRF and designated as “serious.”

Even when only minimal information is available for the initial SAE report, the Investigator should try to make a causality assessment, as the causality is used to determine the timing of regulatory reporting requirements. If the Investigator or designee is not available to sign the SAE report on initial submission, they should be contacted by telephone and their assessment documented on the SAE form (with a note stating signature is forthcoming). The Investigator may change their causality assessment based on follow-up information and submit an amended SAE report form. All efforts will be made to obtain accurate and complete medical records for the SAE. All efforts to obtain information should be documented in the subject’s source documents.

The site will notify the Independent Ethics Committee (IEC)/Institutional Review Board (IRB) according to its guidelines.

The subject’s condition will be followed by the Investigator or designated Subinvestigator until resolution of the condition or a return to baseline levels. If additional visits are required, the subject will be asked to return to the study site for further follow-up. If the condition is still ongoing at the time the subject exits the study, every effort will be made to continue to follow-up with the subject for a reasonable period of time, as determined by the Investigator or until there is a return to baseline or stabilization of the condition. As additional information becomes available, such as hospital discharge notes and subject medical records, the Investigator will be notified and provided with all relevant information.

All SAE that have not resolved by the end of the study or that have not resolved on discontinuation of the subject's participation in the study must be followed until any of the following occurs:

- The event resolves.
- The event stabilizes.
- The event returns to baseline if a baseline value is available.
- The event can be attributed to agents other than the investigational product or to factors unrelated to study conduct.
- It becomes unlikely that any additional information can be obtained (subject or health care practitioner refusal to provide additional information, lost to follow-up after demonstration of due diligence with follow-up efforts).

Serious AE must be reported within 24 hours to:

[contact]

Email: [contact]

14.8.3 Pregnancy Reporting

Pregnancies are captured if they occur in female subjects or in the sexual partners of male subjects from the time the subject is first exposed to the investigational product and ending at the time of study completion or ET of the double-blind period or the OLE period, whichever is later.

Female subjects must be instructed to discontinue all study drugs and inform the Investigator immediately if they become pregnant during the study. Male subjects must inform the Investigator immediately if their partner becomes pregnant during the study.

The Investigator must report any pregnancy to Allakos within 24 hours of becoming aware of it using the provided pregnancy reporting forms. Female subjects must be immediately discontinued from study drug. An uncomplicated pregnancy will not be considered an AE or SAE, but all pregnancies in subjects who received lirentelimab will be followed through term. For male subjects with female partners who become pregnant, the site will ask the father (the study subject) to provide information about the outcome of the pregnancy and information about the baby. If detailed health information about the mother is requested by Allakos, a Pregnant Partner Information Release Form will be provided to the site for the mother to sign.

Any congenital abnormalities noted at birth in the offspring of a subject who received lirentelimab will be reported as a SAE. If the subject received lirentelimab, the outcome of any pregnancy and the presence or absence of any congenital abnormality will be recorded in the

source documentation and reported to the Medical Monitor and Sponsor via the pregnancy reporting form.

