- During the screening period, the EASI, [REDACTED] will be determined, and a baseline will be established.
- If subjects meet eligibility criteria, the Interactive Response Technology (IRT) system will assign subjects 1:1 to receive 7 doses of 300 mg lirentelimab SC or placebo SC. Subjects will be stratified based on biologic-naïve vs biologic-exposed status and IGA score at baseline.
- Eligible subjects will receive the first dose of lirentelimab SC or identical placebo on Day 1. If the study drug is well tolerated (no stopping rules being met), subjects will receive additional doses of lirentelimab SC or placebo SC on Days 15 (Dose 2), 29 (Dose 3), 43 (Dose 4), 57 (Dose 5), 71 (Dose 6), and 85 (Dose 7).
- Subjects will be given an option of entering the OLE period to receive 7 additional doses of open-label study drug.
- Subjects will be followed for 12 additional weeks or 84 days after last dose if ET, after the double period or the OLE period.
- Subjects will remain at the site for at least 1 hour of observation following the end of the SC injection.
- Subjects will complete a number of assessments and questionnaires, including daily ePRO, throughout the duration of the study.
- Total study duration is approximately 7 months for the double-blind period and 9 months if the subject chooses to enter the OLE period.

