- 13) Female subjects must be either postmenopausal (defined as no menses for 12 months without an alternative medical cause) with FSH level >30 mIU/mL at screening or surgically sterile (tubal ligation, hysterectomy, or bilateral oophorectomy) for at least 3 months, or if of childbearing potential, have a negative serum pregnancy test and agree to use a highly effective method of contraception as defined in this protocol or abstain from sexual activity, if compliant with preferred and usual lifestyle of the subject, from screening until the end of the study or for 120 days following the last dose of study drug, whichever is longer.

In the case of a postmenopausal female subject with FSH level ≤ 30 mIU/mL at screening, the subject will be required to have a negative serum pregnancy test during the screening period and will also be required to have a negative urine dipstick pregnancy test prior to dosing and at each study visit.

- 14) Male subjects with female partners of childbearing potential must agree to use a highly effective method of contraception as defined in this protocol or abstain from sexual activity from screening until the end of the study or for 120 days following the last dose of study drug, whichever is longer. All fertile men with female partners of childbearing potential should be instructed to contact the Investigator immediately if they suspect their partner might be pregnant (e.g., missed or late menstrual period) at any time during study participation.

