9.3 Rescue Medications

The use or initiation of any topical or systemic therapy for the purpose of treating AD at any point in the study will be considered rescue therapy. Rescue medications are not allowed during the study unless medically necessary at the discretion of the Investigator (i.e., to treat flare-ups of AD symptoms). Rescue treatment for AD symptoms with otherwise prohibited medications may be provided to study subjects at the discretion of the Investigator.

Study subjects requiring topical rescue therapy within the first 4 weeks of Dose 1 of the double-blind period will be discontinued from the study but will be followed for 12 weeks. Subjects

requiring topical rescue therapy after the first 4 weeks following Dose 1 will continue with the dose regimen and be followed through the end of study.

Study subjects requiring systemic rescue therapy during any point in the double-blind period of the study will be discontinued from the study but will be followed for the 12-week follow-up period.

10. Study Treatment

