12.3.2 Pregnancy Test and Follicle-Stimulating Hormone

A serum pregnancy test (hCG level) will be completed for all female subjects of childbearing potential at screening. Women who are surgically sterile (tubal ligation, partial or total hysterectomy, or bilateral oophorectomy) for at least 3 months or those who are postmenopausal for at least 1 year with FSH level >30 mIU/mL are not considered to be of childbearing potential. At screening, FSH levels will be tested on female subjects to confirm postmenopausal status. Both FSH and hCG samples will be processed by the central laboratory.

Subjects with FSH levels ≤ 30 mIU/mL will be considered to be of childbearing potential. Blood will be collected for serum pregnancy test at screening. Urine will be collected for dipstick pregnancy test on all dosing days, Day 8, and all follow-up days (14, 56, and 84 days after last dose of study drug if ET) for all subjects of childbearing potential. Test kits will be supplied by the central laboratory. Tests will be completed on site and evaluated prior to each SC injection. If a subject has a positive pregnancy test, dosing will immediately be discontinued.

To ensure subject safety, each pregnancy in a subject that received study drug must be reported within 24 hours of learning of its occurrence. If the subject received lirentelimab SC, the pregnancy should be followed to determine outcome, including spontaneous or voluntary termination, details of the birth, and the presence of absence of any birth defects, congenital abnormalities, or maternal and/or newborn complications. If the subject received lirentelimab SC, any SAE experienced during pregnancy must be reported on the SAE Report Form.

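### Pregnancy capture closes about 36 days before the protocol's own contraception requirement ends

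*Protocol*

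**What the plan says.** **Capture window.** Protocol 14.8.3 covers pregnancies in female subjects and in partners of male subjects, starting with a subject's first dose of "investigational product and ending at the time of study completion or ET of the double-blind period or the OLE period, whichever is later".

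**Contraception.** Inclusion criteria 13 (women) and 14 (men with partners of childbearing potential) in 8.4 require contraception or abstinence "from screening until the end of the study or for 120 days following the last dose of study drug, whichever is longer".

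**What subjects are told to report.** Section 14.8.3 limits the instruction to pregnancies arising in the study; for men it reads "Male subjects must inform the Investigator immediately if their partner becomes pregnant during the study". Criterion 14 asks men to make contact if a partner "might be pregnant (e.g., missed or late menstrual period) at any time during study participation".

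**Testing.** Section 12.3.2 sets the schedule: "Urine will be collected for dipstick pregnancy test on all dosing days, Day 8, and all follow-up days (14, 56, and 84 days". The bracketed day counts are for early terminators, and day 84 is the last time point.

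**Length of follow-up.** Section 5.1 says "Subjects will be followed for 12 additional weeks or 84 days after last dose if ET". Subjects taken off for systemic rescue therapy "will be discontinued from the study but will be followed for the 12-week follow-up period" (9.3). Section 15.1 counts a subject as having completed the relevant period at Day 169 or OLE Day 169.

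**Text with no end date.** Section 12.3.2 says "each pregnancy in a subject that received study drug must be reported within 24 hours of learning of its occurrence", and 14.8.3 has its own 24-hour duty for pregnancies the investigator becomes aware of.

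**The concern.** Requiring contraception to 120 days means the protocol regards pregnancy as something to avoid until then. Exclusion criterion 22 points the same way, since it equates five half-lives with four months. The phrase about whichever period is longer in criteria 13 and 14 also allows for the 120 days outlasting the study. Yet the capture window, the last scheduled test and both notification instructions stop at the end of follow-up, before that period is over.

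At stake is the completeness of the pregnancy record. Section 14.8.3 commits the sponsor to follow pregnancies in lirentelimab-treated subjects through term, which is possible only for pregnancies that are identified. The window may also affect unblinding: 11.4 lets a site break the blind for a pregnancy within the pregnancy reporting period. If that means the 14.8.3 window, a later pregnancy falls outside that ground, although the emergency and regulatory grounds remain.

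**Working it through.** **Inputs**

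- Last dose: Day 85 or OLE Day 85 (schedules of assessments; 13.9; 20.11.1).
- Final visit: Day 169 or OLE Day 169, ±5 days (13.12; 20.11.1).
- Contraception: at least 120 days after the last dose (8.4, criteria 13 and 14).
- Close of capture: study completion or ET (14.8.3), read at subject level as in 15.1.

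**Step 1: reproduce the protocol's follow-up length.** 169 − 85 = 84 days, in both periods. This agrees with the 84 days stated in 13.12 and 5.1.

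**Step 2: the gap.** Gap = 120 − days from last dose to close of capture.

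| Final visit, days after last dose | Gap (days) |
|---|---|
| 84 (planned) | 120 − 84 = 36 |
| 89 (84 + 5) | 120 − 89 = 31 |
| 79 (84 − 5) | 120 − 79 = 41 |

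If the Day 85 and Day 169 windows are used independently, the interval runs from 164 − 90 = 74 to 174 − 80 = 94 days, and the gap from 120 − 94 = 26 to 120 − 74 = 46 days.

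**Step 3: subjects who leave follow-up early.** The plan is to follow early stoppers to day 84, so 36 days applies to them too. If the last visit were the 56-day or 14-day one, the gap would be 120 − 56 = 64 or 120 − 14 = 106 days. The documents do not say how many subjects to expect in this group.

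**Step 4: does any scheduled contact fall inside the gap?** Only for OLE subjects whose lymphocyte or eosinophil counts have not recovered by OLE Day 169. The protocol gives two intervals for their extended visits:

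- 20.11.1, about every 28 days: 84 + 28 = day 112, 8 days before day 120.
- Table 8 note 2, every 14 (±5) days: 84 + 14 = day 98 and 84 + 28 = day 112, which are 22 and 8 days before day 120.

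The listed content is a blood count, adverse events of special interest and serious adverse events (SAEs). Section 14.8.3 treats an uncomplicated pregnancy as neither an AE nor an SAE, so SAE collection would not record one. These visits also come after the subject counts as having completed the OLE, and the double-blind schedule has no equivalent.

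**Step 5: check against the protocol's half-life statement.** Taking four months as 120 days, five half-lives give a half-life of 120 / 5 = 24 days. Day 84 is then 84 / 24 = 3.5 half-lives, with 0.5^3.5, or about 9%, remaining under simple first-order decay.

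**The case against.** **Study completion may be a trial-level date.** Section 13.13 defines the end of each period by the last subject's last follow-up visit, and 15.1 also gives a trial-level definition of completion. On that reading, earlier enrollees are covered for longer. Section 13.13 puts the last follow-up at about 24 weeks after enrollment without the OLE and up to 38 weeks with it. Capture could therefore continue for up to 38 − 24 = 14 weeks (98 days) after the last double-blind-only subject finishes, which exceeds 36 days. The ambiguity is real. The subject-level reading is still the more natural one, because 14.8.3 pairs completion with ET, which happens to a subject. The trial-level reading would also leave uncovered the OLE subjects who finish within 36 days of the last OLE visit, and subjects who terminate early.

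**Reporting has no stated cut-off once a pregnancy is known.** This stands. The 24-hour duties, follow-up through term and the rule that a congenital abnormality is an SAE carry no end date. The 12.3.2 sentence names only subjects, but the duty in 14.8.3 can be read to include partners. All of these operate only after someone tells the site; none creates an enquiry or asks subjects to report after their last visit.

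**Nothing requires the two windows to match, and few cases are expected.** Both points are fair. As an illustration, assume the effectiveness figures in 12.3.3 are annual and, as a ceiling, that all 130 subjects are at risk themselves or through a partner. Expected pregnancies in 36 days are 130 × 0.01 × 36/365 = 0.13 at 1% failure and 130 × 0.09 × 36/365 = 1.15 at 9%. If half are at risk, the range is 0.06 to 0.58. These counts include the placebo arm. The mouse reproductive study in 2.2 found no drug-related effects. This limits the importance of the gap without closing it.

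**The consent form or pregnancy forms may cover it.** Possibly; they were not available.

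**Conclusion.** The concern holds as a minor gap in safety capture. On the subject-level reading of 14.8.3, about 36 days (31 to 41 with the ±5-day window) lie between the close of capture and the end of required contraception, with no scheduled pregnancy test, enquiry or instruction to report. The gap is longer for anyone who leaves follow-up before day 84, and shorter or absent for earlier enrollees if completion is read at trial level. The documents do not give the number of lirentelimab-treated subjects who are at risk of pregnancy or have a partner at risk. No efficacy result or main safety conclusion changes. The amendment is still worth making, because the protocol's own 120-day figure exposes the mismatch and correcting it takes little effort.

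**What to change.** - In 14.8.3, end capture at study completion or ET, or 120 days after the last dose, whichever is later.
- Give the notification sentences in 14.8.3 and inclusion criterion 14 the same end date.
- At the last visit, remind subjects to report any pregnancy in themselves or a partner through day 120.

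Two additions are optional: a telephone call at day 120, and a pregnancy question in the extended OLE visit content of Table 8 note 2.

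The cost is protocol wording, one reminder and slight site follow-up after the last visit. No new visit or test is needed. The gain will be small for subjects who withdraw or are lost to follow-up.
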